### 10.1. Adverse Events

#### 10.1.1. Definition of Adverse Event

An Adverse Event (AE) is defined as any untoward medical occurrence, unintended disease or injury, or untoward clinical signs (including abnormal laboratory findings) in patients, users or other persons, whether or not related to the investigational medical device. (ISO 14155:2011 3.2)

The following information regarding each AE will be obtained: date and time of onset and resolution (duration), severity, whether it was serious, any required treatment or action taken, outcome, relationship to the investigational device, relationship to the procedure, and whether the AE caused withdrawal from the study. Hypoglycemic events, as defined in the protocol, will be summarized and compared between the 2 randomized treatment groups.

### 10.1.2. Handling of Missing or Partial Adverse Event Dates

Handling of Missing AE Start-dates (missing AE stop-dates are not filled)

Rules for assuming a full date for AEs with incomplete or missing start-dates are addressed below. In the unusual case that the month portion of an AE start-date is missing but the day portion is not missing, the day portion of the AE will be assumed to be missing. Likewise in the case where the year portion of an AE start-date is missing but the month and/or day portion is not missing, the month and/or day portion of the AE will be assumed to be missing. All missing portion(s) of the AE start-dates will be handled using the same rules.

- In the event that the day portion (and only the day portion) of the AE onset date is missing:
  - o If the AE started in the same month and year as the study procedure, the AE onset date will be assumed to be the date of the study procedure (*i.e.*, Study Day 1);
  - Otherwise, the AE onset date will be assumed to be the 15th day of the given month and year, e.g., XX–DEC-2005  $\rightarrow$  15-DEC-2005 where XX represents an unknown value.
- In the event that the day and month portion (and only the day and month portion) of the AE onset date are missing:
  - o If the AE started in the same year as the study procedure, the AE onset date will be assumed the study procedure (*i.e.*, Study Day 1);
  - Otherwise, the AE onset date will be treated as June 15th of the given year, e.g., XX-XXX-2005 → 15-JUN-2005.

• In the event that the day, month, and year portion of the AE onset date are missing, the start-date of the AE will be assumed to be the study procedure (*i.e.*, Study Day 1).

### Special Cases on Missing AE Start-dates

- If the assumed AE onset date using the above rules for handling of missing AE dates
  - o is earlier than the screening date, the assumed AE onset date will be reset and assumed to be the screening date.
  - o is later than the reported AE stop-date, the assumed AE onset date will be reset and assumed to be the AE stop-date.
  - o is later than the database lock date and AE stop-date missing, the AE will be assumed to be a follow-up AE and not treatment-emergent.

### Several Examples of Handling Missing AE Start-dates

Assume that the study procedure for a patient is 04-FEB-2005 and the Screening Date is 18-JUL-2004

- Example: The day portion (and only the day portion) of the AE onset date is missing:
  - o If the AE onset date is XX-DEC-2004 then the assumed AE onset date is 15-DEC-2004.
  - o If the AE onset date is XX-FEB-2005 then the assumed AE onset date is 04-FEB-2005, as the AE started in the same month and year as the study procedure.
- Example: The day and month portion (and only the day and month portion) of the AE onset date are missing
  - o If the AE onset date is XX-XXX-2004:
    - then the assumed AE onset date is 15-JUN-2004 using the rules;
    - but this is a special case since the assumed date 15-JUN-2004 is before the patient's screening date 18-JUL-2004. Therefore, the assumed AE onset date will be reset and assumed to be 18-JUL-2004.
  - o If the AE onset date is XX-XXX-2005 then the assumed AE onset date is 04-FEB-2005, as the AE started in the same year as the study procedure.
- Example: The day, month, and year portion of the AE onset date are missing (*i.e.*, if the AE onset date is XX-XXX-XXXX), then the assumed AE onset date is 04-FEB-2005).

### 10.1.3. Summaries of Adverse Events

All summaries of adverse events will be based on events that occurred during the study and reported for the ITT population. Adverse events will be mapped to preferred terms and body systems using the Medical Dictionary for Regulatory Activities (MedDRA) coding dictionary. The number and percentage of patients experiencing 1 or more adverse events will be presented by preferred term using counts, percentages, and 2-sided 95% exact binomial confidence intervals. The relationship of the adverse event relative to the *device* and *procedure* will be presented

Version 1.0 Confidential Page 37 of 42

separately. The number and percentage of patients experiencing 1 or more events will be presented by the event description using counts, percentages, and 2-sided 95% exact binomial confidence intervals.

Table 14.3.2 entitled *Overall Summary of Adverse Events (ITT Population)* contains the primary presentation of the adverse event data, independent of the type of event. This table is prepared without regard to causality or relationship to the study procedure or device. Patients will be counted only once for each event type; multiple occurrences of the same event type for a patient will only be counted once. Event types will be displayed alphabetically. The overall incidence of adverse events will be summarized using counts, percentages, and 2-sided 95% exact binomial confidence intervals.

Table 14.3.3 entitled Summary of Adverse Events by Event Type (ITT Population) contains the primary presentation of the adverse event data. This table is prepared without regard to causality or relationship to the study procedure or device. Patients will be counted only once for each event type; multiple occurrences of the same event type for a patient will only be counted once. Event types will be displayed alphabetically. The overall incidence of adverse events will be summarized using counts, percentages, and 2-sided 95% exact binomial confidence intervals.

Table 14.3.4 entitled Summary of Post-Procedural Adverse Events by Event Type and Relationship to the Study Device (ITT Population) provides the presentation of adverse events by relationship to study device. This table will have the same structure as that of Table 14.3.2, however, only those adverse events that were determined to be related to study device will be displayed. Patients with multiple occurrences of the same event will be summarized using the strongest relationship to study device. The number and percentage of patients experiencing each event type will be displayed.

Table 14.3.4a entitled Summary of Post-Procedural Adverse Events by Event Type and Relationship to the Study Device by Device Generation, Voltage, and Single vs. Double Treatment (ITT Population) provides the presentation of adverse events by relationship. This table will follow the Level 2a format for the IS population and Level 2b format for the population. Patients with multiple occurrences of the same event will be summarized using the strongest relationship to study device. The number and percentage of patients experiencing each event type will be displayed.

Table 14.3.5 entitled Summary of Post-Procedural Adverse Events by Event Type and Relationship to the Study Procedure (ITT Population) provides the presentation of adverse events related to the study procedure. This table will have the same structure as that of Table 14.3.2, however, only those adverse events that were determined to be related to the study procedure will be displayed. Patients with multiple occurrences of the same event will be summarized using the strongest relationship to study procedure. The number and percentage of patients experiencing each event type will be displayed.

Table 14.3.5a entitled Summary of Post-Procedural Adverse Events by Event Type and Relationship to the Study Procedure by Device Generation, Voltage, and Single vs. Double Treatment (ITT Population) provides the presentation of adverse events by relationship. This table

will follow the Level 2a format for the IS population and Level 2b format for the population. Patients with multiple occurrences of the same event will be summarized using the strongest relationship to study device. The number and percentage of patients experiencing each event type will be displayed.

Table 14.3.5.1 entitled Summary of Post-Procedural Adverse Events by Event Type and Relationship to the Study Device or Procedure (ITT Population) provides the presentation of adverse events related to the study device or the study procedure. This table will have the same structure as that of Table 14.3.2, however, only those adverse events that were determined to be related to the study device or procedure will be displayed. Patients with multiple occurrences of the same event will be summarized using the strongest relationship to study device or procedure. The number and percentage of patients experiencing each event type will be displayed.

Table 14.3.5.1a entitled Summary of Post-Procedural Adverse Events by Event Type and Relationship to the Study Device or Study Procedure by Device Generation, Voltage, and Single vs. Double Treatment (ITT Population) provides the presentation of adverse events by relationship. This table will follow the Level 2a format for the IS population and Level 2b format for the population. Patients with multiple occurrences of the same event will be summarized using the strongest relationship to study device. The number and percentage of patients experiencing each event type will be displayed.

Table 14.3.6 entitled Summary of Adverse Events Leading to Study Discontinuation (ITT Population) displays all adverse events resulting in the completion status defined as premature discontinuation due to an adverse event. This table will have the same structure as Table 14.3.6, however, only those adverse events that led to discontinuation will be displayed. Patients will be counted only once by event type; multiple occurrences of the same event for a patient will be counted only once. The number and percentage of patients experiencing each type of event leading to premature discontinuation will be displayed.

Listing 16.7.2 entitled *Adverse Events* provides supportive data for Tables 14.3.1 through 14.3.6 and is sorted by site number and patient number. Listing 16.7.3 entitled *Serious Adverse Events* is a subset of 16.7.2 and contains just the serious events; this listing will be sorted by site number and patient number.

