This visit will be performed onsite. The following evaluations/procedures are to be performed. Participant's study eligibility will be reconfirmed at this visit.

- Physical examination
- Anthropometric measurements including height, weight and waist circumference
- Vital signs
- Adverse event (changes in medical history)
- Concomitant medications
- 12-lead EKG
- Laboratory tests:
 - o Hematology (CBC with differentials)
 - Metabolic panel
 - o Glycemic parameters (HbA1C, MMTT, HOMA-IR)
 - Fasting lipid panel
 - o Lipase, Amylase
 - o Serum iron, ferritin, transferrin, saturation, serum folate, Vitamin D, Vitamin B12
 - o International normalized ratio (INR) for participants on Warfarin (may be performed on Day 0)
- H. Pylori breath or stool test
- Pregnancy test for females capable of becoming pregnant
- Assessment for eligibility
- Preparation with gastroenterologist for procedure, medication management per Section 6.
- Diabetes education, including instruction on CGM use
- Treating physician review of diabetes history and titration of glucose-lowing medications per Section 6.2
- Review CGM data
- Lifestyle counselling

If the participant is no longer eligible for the study due to a change in the participant's condition, such as pregnancy, abnormal blood test values, HbA1C outside of the protocol range, or weight change resulting in a BMI outside of the protocol range, the participant will be excluded from the study and documented as a screen failure.

The screening and baseline visit may be combined if the screening visit falls within the baseline visit window. In this case, data collected during the combined visit will serve as both screen and baseline data.

It is recognized that new COVID-19 restrictions may cause delays in scheduling the index procedure, resulting in the baseline visit out of window. In case the baseline visit is out of visit window, investigator will reassess participant's eligibility by evaluating any changes in participant's medical history and medications, Investigator's assessment will be documented on eCRF. The following tests will be repeated for safety considerations or to serve as baseline data:

- Laboratory tests:
 - Hematology (CBC with differentials)
 - o Glycemic parameters (FPG, HbA1C, insulin, HOMA-IR)
- Pregnancy test for females capable of becoming pregnant (may be performed on Day 0)
- Anthropometric measurements including weight and waist circumference (may be collected on Day
 0)

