12.4.3 Primary Endpoint Analysis

The primary endpoint of the study is the proportion of participants experiencing one or more device- or procedure-related serious adverse events within 12 weeks post-procedure. The analysis will be performed using the ITT population, then tabulated and reported for each treatment arm and overall. Fisher's exact test will be used to assess differences which may be present between groups

Additionally, an overall summary of AEs will be provided including the number of events and percent of participants with any AEs, SAEs, and UADEs. For each type of event, the number of events and number and percent of participants with the event will be provided. Separate summaries of all adverse events will be summarized by seriousness and by relationship to device and procedure.

Only events occurring at or after the index procedure will be counted for the purpose of safety analysis. Events occurring prior to the index procedure will be considered as medical history.

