# 4.2. Endpoints

There is a single primary endpoint predicated on safety and 18 secondary endpoints. The primary safety endpoint is the proportion of patients experiencing device-related or procedure-related serious adverse events within 12 weeks of the procedure.

For a complete presentation of safety, a tabulation of all adverse events over the course of the clinical investigation will be presented. Adverse events will be summarized as follows:

- All adverse events
- All procedure-related adverse events
- All device-related adverse events
- All serious adverse events
- All serious procedure-related adverse events
- All serious device-related adverse events
- All Unanticipated Adverse Device Effects (UADE)
- All Unanticipated Serious Adverse Device Effects (USADE)

The following elements (variable – label) will be presented in the supportive data listing (Ref. Case Report Form)

**AESEV** - Severity

- Mild
- Moderate

Version 1.0 Confidential Page 10 of 42

Severe

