## 5.4. Estimated Duration of Patient Participation

Total duration on study will be calculated as the difference between the date of informed consent and the last on-study observation. All calculations defining the duration on study will be performed relative to the date of informed consent and follow the algorithm DURATION = ([STUDY COMPLETION OR WITHDRAW DATE – INFORMED CONSENT DATE])+1.

The first participant enrolled was in Q4, 2021; the estimated enrollment duration is 18 months.

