### 10.1.4. Summaries of Serious Adverse Events

The tables outline above will be repeated, restricted to just serious adverse events. All summaries of serious adverse events will be based on events that occurred during the study. Adverse events will be mapped to preferred terms and body systems using the Medical Dictionary for Regulatory Activities (MedDRA) coding dictionary. The number and percentage of patients experiencing 1 or more adverse events will be presented by preferred term using counts, percentages, and 2-sided 95% exact binomial confidence intervals. The relationship of the adverse event relative to the device and procedure will be presented separately. The number and percentage of patients experiencing 1 or more events will be presented by the event description using counts, percentages, and 2-sided 95% exact binomial confidence intervals.

- Table 14.3.7 entitled Overall Summary of Serious Adverse Events (ITT Population)
- Table 14.3.8 entitled Summary of Serious Adverse Events by Event Type (ITT Population)
- Table 14.3.9 entitled Summary of Post-Procedural Adjudicated Serious Adverse Events by Event Type and Relationship to the Study Device (ITT Population)
- Table 14.3.10 entitled Summary of Post-Procedural Adjudicated Serious Adverse Events by Event Type and Relationship to the Study Procedure (ITT Population)
- Table 14.3.10.1 entitled Summary of Post-Procedural Adjudicated Serious Adverse Events by Event Type and Relationship to the Study Device or Procedure (ITT Population)
- Table 14.3.11 entitled Summary of Serious Adverse Events Leading to Study Discontinuation (ITT Population)

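### SAP Tables 14.3.2, 14.3.3, 14.3.7 and 14.3.8 set no post-procedure limit, so AEs and SAEs from before exposure can enter them, contrary to Protocol 12.4.3

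*SAP*

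**What the plan says.** **Protocol.** Section 12.4.3 sets the counting rule: "Only events occurring at or after the index procedure will be counted for the purpose of safety analysis". It adds: "Events occurring prior to the index procedure will be considered as medical history". Collection starts earlier than counting. The Schedule of Activities (Appendix 2) marks adverse events and hypoglycaemic episodes at screening and baseline, and the Baseline Visit list in Section 7.13.2 includes an adverse event item, glossed as changes in medical history.

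**SAP.** Section 10.1.3: "All summaries of adverse events will be based on events that occurred during the study and reported for the ITT population". Section 10.1.4: "All summaries of serious adverse events will be based on events that occurred during the study". Section 4.2 is equally broad: "a tabulation of all adverse events over the course of the clinical investigation will be presented". The at-or-after-procedure rule is not restated for these tables.

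**Table titles.** The device- and procedure-relationship tables (14.3.4, 14.3.5, 14.3.5.1, 14.3.9, 14.3.10, 14.3.10.1) are titled as post-procedural. The overall and by-event-type tables (14.3.2 and 14.3.3 for AEs, 14.3.7 and 14.3.8 for SAEs) have no such limit in title or text. The SAP describes both 14.3.2 and 14.3.3 as the primary presentation of AE data.

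**The concern.** The two documents give different windows for the same events, and the SAP is what a programmer will code from. Its wording lets an AE that arose between screening and the procedure be counted in the tables a reader consults first for the device's safety profile. Such an event cannot be caused by a device not yet used.

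The tables would also fail to reconcile. SAP 10.1.3 describes Table 14.3.4 as having the structure of 14.3.2, limited to device-related events, so a reader will take it as a subset. If 14.3.2 runs from screening and 14.3.4 from the procedure, the two cover different periods.

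The hypoglycaemia summary in SAP 10.1.1 has the same gap: it gives no start date, while episodes are recorded from screening.

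**Working it through.** The documents give no event figure to reproduce. The check compares the windows and then sizes the difference.

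**1. Does the SAP wording reach back before the procedure?**
- AEs in the database can have pre-procedure onsets (Appendix 2; Protocol 7.13.2).
- The SAP does not define what counts as during the study for AEs. The term treatment-emergent appears once, under the special cases for missing AE start-dates, without a definition and not as a table filter.
- The partial-date rules keep early onsets. If an assumed onset "is earlier than the screening date, the assumed AE onset date will be reset and assumed to be the screening date". The limit is screening, not the procedure. The SAP's example keeps an onset of 15-DEC-2004 for a procedure on 04-FEB-2005.
- A limit appears in the titles of the relationship tables and not in those of the overall tables.

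Taken together, the unrestricted reading is the natural one for 14.3.2, 14.3.3, 14.3.7 and 14.3.8.

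**2. How long is the extra period?** The screening window is day -84 to day -5 (Appendix 2). Follow-up is 48 weeks = 336 days.
- Share = pre-days / (pre-days + 336).
- Shortest: 5/341 = 1.5%.
- Screening combined with baseline, at most 21 days: 21/357 = 5.9%.
- Longest in window: 84/420 = 20.0%.

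**3. Effect of one patient, with no rate assumed.** Take a patient whose only event came before the procedure. Intervals are exact binomial 95%, the SAP's method.

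| Group | Without | With | Added |
|---|---|---|---|
| All, n=20 | 0/20 = 0% (0 to 16.8) | 1/20 = 5% (0.1 to 24.9) | 5 points |
| 750 V double, n=10 | 0/10 = 0% (0 to 30.8) | 1/10 = 10% (0.3 to 44.5) | 10 points |
| 600 V double, n=7 | 0/7 = 0% (0 to 41.0) | 1/7 = 14.3% (0.4 to 57.9) | 14.3 points |
| 600 V single, n=3 | 0/3 = 0% (0 to 70.8) | 1/3 = 33.3% (0.8 to 90.6) | 33.3 points |

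**4. Expected number added to the overall AE percentage.** Assumptions, not in the documents: a constant background rate r of 1 to 2 AEs per patient-year, the same before and after the procedure, and a full 84 days for everyone. A patient is added only with at least one AE before the procedure and none after it:

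P(added) = [1 − exp(−r × 84/365.25)] × exp(−r × 336/365.25)

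- r = 1: 0.205 × exp(−0.920) = 0.082, or 1.6 of 20.
- r = 2: 0.369 × exp(−1.840) = 0.059, or 1.2 of 20.

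A single event-type row can gain more, because a patient with a later AE of another type is still new to that row.

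**5. Would a date filter alone work?** Not with the SAP's two onset rules. Take the SAP's example procedure date, 04-FEB-2005, and an AE with onset known only as February 2005.
- SAP 7.3.4, which covers medical events including AEs, uses the first of the month: 01-FEB-2005. The filter drops the event.
- SAP 10.1.2 uses the procedure date: 04-FEB-2005. The filter keeps it.

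They also differ on a wholly missing onset date: 7.3.4 imputes nothing, and 10.1.2 assigns the procedure date.

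**The case against.** The best reply is that the protocol rule still applies. SAP Section 3 says the SAP is to be read with the protocol, and nowhere does the SAP say that earlier events will be counted. Its study days run from the procedure, enrolment occurs on procedure day, and Table 14.3.4 is said to differ from 14.3.2 only by relatedness, which hints at a common window. The example dates look generic: screening on 18-JUL-2004 and procedure on 04-FEB-2005 are 201 days apart, well outside this trial's 84.

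Much of this is fair. The case is an omission combined with broader wording, not an express reversal of the protocol. But a general cross-reference does not narrow a sentence that says all summaries use events during the study, and limiting some titles but not others points the other way.

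A reader might infer more than the documents support:
- **That the SAP dates AEs from consent.** SAP 5.4 says "All calculations defining the duration on study will be performed relative to the date of informed consent", but that defines one variable, time on study. It does not define the AE window.
- **That the primary endpoint is contaminated.** SAP Section 9 counts from the start of the procedure to study day 84.
- **That discontinuation rates are distorted.** A patient who leaves before enrolment is a screen failure, so Tables 14.3.6 and 14.3.11 are essentially unaffected. Any exception would come from the wider ITT definition in SAP Section 10, which is a separate matter.
- **That severe hypoglycaemia is inflated.** A severe event since screening excludes the patient (criterion 42). The gap concerns the non-severe episodes kept on their own form.
- **That 4 to 7 of 20 patients would be added.** That is 20 × 0.205 to 20 × 0.369, the patients with any pre-procedure AE after a full 84 days. Most would have a later AE and be counted anyway.

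The listings also show days relative to the procedure, so early events can be identified. That helps an auditor but does not correct the tables.

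**Conclusion.** The point holds for four tables: 14.3.2, 14.3.3, 14.3.7 and 14.3.8. As written, the SAP lets events from before exposure into its primary AE presentation, against Protocol 12.4.3, and gives those tables a different window from the relationship tables. The hypoglycaemia summary needs the same clarification.

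The size is modest overall and larger in small groups. The per-patient shifts assume no rate, only a patient whose sole event came early. The figure of 1.2 to 1.6 patients rests on the assumed rate and on the longest in-window screening period. Shorter screening lowers it. A screening visit that falls out of window, which Protocol 7.13.1 tolerates for COVID-19 delays, would raise it. The analysis is descriptive, so no formal test is at risk. What is at risk is an AE profile that does not match the protocol's definition or the SAP's other tables. It should be corrected.

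**What to change.** 1. In SAP 10.1.3 and 10.1.4, state that all AE and SAE tables count events with onset at or after the start of the index procedure, as in Protocol 12.4.3 and with the same start that SAP Section 9 uses for the primary endpoint. Report earlier events as medical history in a separate listing.
2. In SAP 10.1.1, give the hypoglycaemia summary the same start.
3. For AE onset dates, replace the SAP 7.3.4 rule with the SAP 10.1.2 rule, so that the filter keeps events with a partial or missing onset date that may have followed the procedure.

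**Cost.** A few sentences in the SAP, one onset-date filter in the AE programs and one extra listing. No new data and no protocol amendment are needed. Items 1 and 3 should be made together, since the filter without the date rule could drop genuine post-procedure events.

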9.2 Device Relationship (Causality)

Causality assessment is required for AEs (and SAEs) that occur during clinical investigations. The following terms will be used during this study:

- Related An AE that is directly and clearly related to the Investigational Device
- Possibly Related There is a reasonable likelihood that the event is due to the Investigational Device, as evidenced by the following:
 - There may be temporal association with the Investigational Device (e.g., within 24 hours of the DMR procedure)
 - The event, or level of severity of the event, is unlikely to be explained by other etiologies (known to be related to the study disease, patient's baseline medical condition, or concomitant medications)
- Unlikely Related The AE is not temporally related to the Investigational Device, or is known to be related to one of the following:
 - Morbidity associated with underlying medical condition
 - Anesthesia
 - Upper GI endoscopy
 - Concomitant medication
 - A relationship to the Investigational Device is not biologically plausible
- Not related The AE is definitely not related to the Investigational Device

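### By-group Tables 14.3.5a and 14.3.5.1a collapse repeat adverse events on the device relationship, so they can understate the procedure relationship and disagree with their parent tables

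*SAP*

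**What the plan says.** SAP 10.1.3 sets a collapsing rule table by table for patients with repeat occurrences of one event.

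- **Tables 14.3.4 and 14.3.4a** (relationship to device, overall and by group): "Patients with multiple occurrences of the same event will be summarized using the strongest relationship to study device". Here the rule fits the subject.
- **Table 14.3.5** (relationship to procedure, overall): "Patients with multiple occurrences of the same event will be summarized using the strongest relationship to study procedure". This table is also restricted to events judged procedure-related.
- **Table 14.3.5a** is titled "Summary of Post-Procedural Adverse Events by Event Type and Relationship to the Study Procedure by Device Generation, Voltage, and Single vs. Double Treatment". Its rule is nevertheless the device sentence used for 14.3.4 and 14.3.4a.
- **Table 14.3.5.1** (device or procedure, overall): "Patients with multiple occurrences of the same event will be summarized using the strongest relationship to study device or procedure". It too is restricted to related events.
- **Table 14.3.5.1a** (device or procedure, by group): the device sentence again.

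No relatedness filter is stated for either by-group table. SAP 4.2 lists the relationships to device (AEDREL) and to procedure (AEPREL) as separate items, each with four levels: definitely, possibly, unlikely and not related. Nothing elsewhere in the SAP overrides the rule.

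**The concern.** A table about the procedure relationship should choose its record on the procedure grade. The device grade cannot stand in for it. Protocol 9.2 describes one device category as "Unlikely Related The AE is not temporally related to the Investigational Device, or is known to be related to one of the following", and the list that follows includes anesthesia and upper GI endoscopy. An event from those causes can therefore sit low on the device scale while being attributable to the procedure. Selecting on device can pass over it in favour of another occurrence. The rule also gives no answer when the device grades tie and the procedure grades differ.

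At stake is whether the report agrees with itself. The Level 2a and 2b layouts in SAP 7 carry an All Patients column, which for the same ITT population should match the parent table. These are also the tables that break related events down by device generation, voltage and single or double treatment. Repeat occurrences are plausible: Protocol 2.5.2 lists abdominal pain, nausea and vomiting as anticipated.

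**Working it through.** There is no planned figure to reproduce, because this is a tabulation rule. The check enumerates what the rule does.

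**Inputs.** Four device levels and four procedure levels (SAP 4.2); group sizes 3, 7 and 10, total 20 (SAP 3).

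**Assumptions.** 'Related' means definitely or possibly; the SAP gives no cut-off for these tables, but Protocol 9.1 defines an adverse device effect in that way. Device ties are resolved in the SAP's favour.

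**An example that does not depend on order.** A patient has nausea twice: (device possibly, procedure possibly) and (device unlikely, procedure definitely).
- Table 14.3.5 shows definitely.
- Table 14.3.5a keeps the first occurrence and shows possibly. Both occurrences are procedure-related, so filtering before or after selection makes no difference.

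**An example that does depend on order.** Nausea twice: (device unlikely, procedure definitely) and (device possibly, procedure not related).
- Table 14.3.5 shows definitely.
- If Table 14.3.5a selects first, it keeps the second occurrence. A later filter removes it; with no filter it sits in a not-related row.
- If the table is first limited to procedure-related occurrences, only the first remains and the result is correct.

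**Enumeration for Table 14.3.5a.** Two occurrences give 4^4 = 256 patterns.
- Of the 16 procedure pairs, 2 × 2 = 4 have neither occurrence related. So (16 − 4) × 16 = 192 patterns have a procedure-related occurrence.
- For a given occurrence, 6 of the 16 device pairs give it the strictly higher device grade.
- *Lost if selection comes first:* the occurrence with the higher device grade is unrelated to the procedure (2 levels) and the other is related (2 levels), in either order: 2 × 2 × 2 × 6 = 48 of 192.
- *Downgraded from definitely to possibly:* procedure grades are definitely and possibly, with the possibly occurrence higher on device, in either order: 2 × 6 = 12 of 192. This count is the same whether selection or filtering comes first.
- *Filter first:* 0 lost, 12 downgraded.

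**Enumeration for Table 14.3.5.1a.** Patterns with any related grade: 256 − 2^4 = 240.
- *Reporting the device grade itself:* lost when both device grades are unrelated but a procedure grade is related, 4 × 12 = 48; downgraded when the best device grade is possibly and the best procedure grade is definitely, 5 × 7 = 35.
- *Selecting the occurrence by device, then reporting the higher of its two grades:* downgraded in 14. The retained occurrence's higher grade is possibly, and the discarded one is definitely procedure-related with a lower device grade: 6 + 1 = 7 combinations, in two orders. Here 6 = 3 procedure grades × 2 lower device grades when the retained device grade is possibly; 1 is the case of retained (device unlikely, procedure possibly) and discarded (device not related, procedure definitely).
- *Lost under that second reading:* 2 × 2 × 2 = 8 if selection comes first, 0 if filtering comes first. To be lost, the retained occurrence is device unlikely with an unrelated procedure grade, and the discarded one is device not related with a related procedure grade.

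These are counts of logical patterns, not expected frequencies.

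**Weight of one patient.** 1/3 = 33.3%, 1/7 = 14.3%, 1/10 = 10.0%; overall 1/20 = 5.0%.

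**After correction** each by-group rule is identical to its parent's, so discordant patterns fall to 0.

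**The case against.** The strongest reply is that little depends on this. The tables are descriptive; SAP 7.1 calls testing informative only and SAP 9 says there are no formal hypothesis tests. The rule acts only when one patient has the same event at least twice with grades that cross. Most patterns agree even in the enumeration: 60 of 192 (48 + 12) are discordant if selection comes first, 12 of 192 if filtering does. The percentages per patient are simply 1/n. If the table is filtered first and shows only counts by event type, with no grade rows, nothing moves. All of that stands, and it limits the size of the point.

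Four stronger readings are tempting but are not supported.

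- **That the primary endpoint is affected.** SAP 9 counts all device- or procedure-related serious events through day 84, and SAP 9.1 analyses one binary variable per patient. Neither uses the collapsing rule.
- **That the serious-event tables inherit the error.** SAP 10.1.4 says "The tables outline above will be repeated, restricted to just serious adverse events", but the list beneath it names no by-group versions. The relationship tables it does name correspond to the overall tables. Carry-over is possible, not established.
- **That events are dropped.** This requires selection before filtering, and the SAP states no order.
- **That the rule usually keeps the wrong occurrence.** Protocol 9.2 grades device causality only, and no criteria for procedure causality are given. How often the two grades cross is unknown.

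None of this makes the stated rule right. It contradicts the tables' titles and their parents, and a programmer must either follow it or depart from the SAP without saying so.

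**Conclusion.** Wrong as written, in two tables. Tables 14.3.5a and 14.3.5.1a use a device-based rule where their titles and parents call for procedure, and for device or procedure. The device sentence looks like a carry-over from Table 14.3.4a.

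Followed literally, it can show a patient's procedure relationship as weaker than the parent table does, and so make the All Patients column disagree with the parent. Under either order of filtering and selection, downgrading is possible wherever relationship grades are displayed; loss from the related rows occurs only if selection comes first. These statements assume that related means definitely or possibly.

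The effect is confined to these descriptive by-group tables. The overall tables have the right rule, and the adverse-event listing should let a reader trace any discrepancy, since SAP 4.2 includes both relationships among the listed items.

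**What to change.** - In Table 14.3.5a, replace *study device* with *study procedure* in the collapsing rule.
- In Table 14.3.5.1a, replace it with *study device or procedure*, and say that this means the higher of the two grades.
- State that both by-group tables apply the same relatedness filter as their parents.
- If by-group serious-event versions are produced under SAP 10.1.4, use the corrected rule there as well.

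The cost is a few words in the SAP and one line of derivation code. There is no analytical downside.
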